10.3.3.4. Follow-Up of AEs and SAEs

The PI (or designee) should employ best medical judgment in determining how to manage AEs and SAEs. Any questions regarding AE or SAE management should be directed to the Medical Monitor.

Investigator Follow-Up

Any ongoing study drug-related SAEs or severe TEAEs present at the time of study termination for the patient (EOS visit or early termination) will be followed until resolved or until the event stabilizes and the overall clinical outcome has been ascertained or is not considered to be of clinical significance. All other TEAEs considered related to study drug and SAEs considered not related to study drug will be followed for up to 30 days after the later of the EOS/ET visit or the last dose of study drug. During the study period, resolution of AEs (with dates) should be documented on the AE eCRF and in the patient's medical record to facilitate source data verification. For the subjects who withdraw consent, the SAEs, severe TEAEs, and other TEAEs considered related to the study drug will be followed until the date of withdrawal of consent. The withdrawal of consent date will be recorded as the end date of the event.

Sponsor Follow-Up

For SAEs, AESIs, and pregnancies, the Sponsor or a designee may follow up by telephone, fax, electronic mail, and/or a monitoring visit to obtain additional case details and outcome information (eg, from hospital discharge summaries, consultant reports, autopsy reports) in order to perform an independent medical assessment of the reported case. For the subjects who withdraw consent these events will be followed until the date of withdrawal of consent. The withdrawal of consent date will be recorded as the end date of the event.

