10.3.3. Recording and Follow Up of AE and/or SAE

10.3.3.1. AE and SAE Recording

AEs that occur after signing the ICF, but before the first dose of study drug, will be recorded to the eCRF as medical history, unless related to a study procedure.

Any SAE that occurs after signing the ICF, but before the first dose of study drug, will be recorded to the eCRF as an SAE. The PI (or designee) will assess all AEs and SAEs and will record the following information on the appropriate eCRF:

- Date of onset
- Date of resolution or stabilization
- Severity
- Relationship to study drug
- Action taken with study medication

Events that, in the opinion of the PI (or designee), may represent intolerance of the IV infusion of study drug must be recorded as AEs on the eCRF. In general, these events will be temporally related to study drug infusion.

Laboratory abnormalities should not be recorded as AEs or SAEs unless they are associated with clinical signs or symptoms, require medical intervention or lead to interruption of study drug infusion or discontinuation. If the laboratory abnormality is part of a clinical condition or syndrome, it should be recorded as the syndrome or diagnosis rather than as the individual laboratory abnormality. In addition, laboratory abnormalities or other abnormal test assessments (eg, ECGs) that are associated with signs or symptoms must be recorded as AEs or SAEs if they meet the definition of an AE (or SAE) as described in [Section 10.3.1](#) (or [Section 10.3.2](#)).

Additional details can be found in the applicable study plans.

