6.2.1 PARTIAL OR MISSING DATES

Partial or missing dates required to identify treatment-emergent or concomitant data will be imputed.

For partial or missing start and end dates of AEs and concomitant medications, the following rules apply:

Partial or Missing Start Dates:

- Missing Day Only: Impute as the 1st of the month, unless the month and year match the first dose date, then impute the day of the first dose.
- Missing Day and Month: Impute as January 1st, unless the year matches the first dose year, then impute the day and month of the first dose.
- Completely Missing Date: Impute as the first dose date unless the end date is on or before the first dose date; in that case, impute as January 1st of the end date's year.

Partial or Missing End Dates:

- Missing Day Only Impute as the last day of the month, unless the month and year match the last dose date, then impute the day of the last dose.
- Missing Day and Month: Impute as December 31st, unless the year matches the last dose year, then impute the day and month of the last dose.
- Ongoing Flag Missing or "Yes": Do not impute the end date unless a death date is available; then impute as the death date.
- Ongoing Flag "No": Impute the missing end date as the last dose date.
- Lost to Follow-Up or Withdrawal Without End Date: Use the last known participation date as the end date.
- Imputed Date After Death Date: Set the end date equal to the death date.

Original dates will be displayed in data listings, and imputed dates will be used only for derivations (e.g., study day, treatment-emergent status).

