Due to several consent withdrawals and patients declining to re-consent for the 12-month extension, the Sponsor unmasked the clinical team to assess whether early study termination was appropriate. Investigators, the CRO clinical operations team, and CRO statisticians remained masked until the database lock. The following specific changes have been made and the additions are considered exploratory:

- Due to early termination of the study, only proptosis measured by Hertel and Total CAS will be analyzed in tables. Other secondary and exploratory endpoints will be listed.
- Either eye responder analyses have been added for proptosis by Hertel and Total CAS, and either eye continuous analyses have been added for Total CAS. Either eye responder and continuous Total CAS analyses will identify an eye at Week 37 (Day 253) and use that same eye in the analysis for each visit.
- A sensitivity analysis, as defined in protocol Section 9.2.4, has been added for Total CAS in the study eye and separately for either eye. Only the pooled active group will be compared to placebo. The sensitivity analysis of the primary responder rate for proptosis from protocol Section 9.4.2. has been removed.

CONFIDENTIAL

The contents of this document are confidential to [REDACTED]
Unauthorized use, disclosure, or reproduction is strictly prohibited.

- An ANCOVA model has been added to existing mean and mean change from baseline Total CAS tables. The model includes baseline and treatment as factors and will be run separately for each eye (study eye and either eye) and visit. Only the pooled active group will be compared to placebo.
- 95% CI for proptosis responder analysis has been removed
- LOCF has been added as the imputation method for missing data for all efficacy analyses.
- Per Protocol Population analyses have been removed.
- ODO analyses have been added for all proptosis and CAS tables to check robustness of results.

17. References

1. Giner G, Smyth GK (2016). statmod: probability calculations for the inverse Gaussian distribution. R Journal 8(1), 339-351.
2. ICH Harmonised Tripartite Guideline: Statistical Principles for Clinical Trials E9. International Council for Harmonisation of Technical Requirements for Pharmaceuticals for Human Use. 05 February 1998.

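### The AE date rules can record an unresolved serious or related event as ended at consent withdrawal, conflict for withdrawn patients, and can count an event that ended before dosing as treatment-emergent

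*Protocol*

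**What the plan says.** **Protocol.** Section 10.3.3.4, under investigator follow-up, says what happens once consent has been withdrawn: "the SAEs, severe TEAEs, and other TEAEs considered related to the study drug will be followed until the date of withdrawal of consent", and adds "The withdrawal of consent date will be recorded as the end date of the event". The same sentence closes the sponsor follow-up paragraph, which covers SAEs, AESIs and pregnancies. Section 10.3.3.1 lists the items the site records for each AE. The one that closes an event is "Date of resolution or stabilization".

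**SAP 6.2.1, end dates.** If the ongoing flag is Yes or missing: "Do not impute the end date unless a death date is available". If the flag is No: "Impute the missing end date as the last dose date". For patients who left: "Lost to Follow-Up or Withdrawal Without End Date: Use the last known participation date as the end date". An end date lacking the day, or the day and month, falls back on the last dose if the known part matches it. No rule compares the result with onset.

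**SAP 6.2.1, start dates.** A start lacking the day, or the day and month, is set to the first dose if the known part matches it. Only the rule for a completely missing start looks at the end date first.

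**Use of the dates.** SAP 6.2.1 shows original dates in listings and keeps imputed dates for derivations. SAP 12.1 defines a TEAE by onset or worsening on or after first dose, and lists serious and related TEAEs separately. It plans no summary of AE duration or outcome.

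**The concern.** An end date entered on the day consent is withdrawn reads as the day the event resolved or stabilized, although follow-up simply stopped. A patient may withdraw because of an event, so the rule bears on serious and related events whose course matters most. The background in SAP section 16 makes this more than theoretical: "Due to several consent withdrawals and patients declining to re-consent for the 12-month extension" is how it opens its account of why the sponsor unmasked its clinical team to consider stopping.

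The SAP rules raise two further questions: whether two programmers would derive the same end date for a withdrawn patient, and whether TEAE counts in arms of 8 can include events that were over before the first infusion.

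**Working it through.** The days and dates in the examples are assumed. The rules are applied literally.

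**Inputs**
- Last dose Day 337, end of study Day 505 (Protocol synopsis); 7 to 13 doses every 4 weeks (SAP 3.1); 8 patients per randomized arm (SAP Table 1).
- All AEs recorded to Day 365, then only treatment-related ones (Protocol 8.3.1).
- Pre-dose non-serious AEs go to medical history unless procedure-related; pre-dose SAEs are recorded as SAEs (Protocol 8.3.1).
- Screening lasts up to 30 days.

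**(a) Withdrawal date as end date.** SAE onset Day 150, unresolved, consent withdrawn Day 160. The recorded end is Day 160 and the apparent length is 160 − 150 = 10 days. The SAP imputation rules never apply, because the field is not empty. Showing original dates in listings gives no protection, because this is the original date.

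**(b) Conflict for a patient who left with an event still ongoing**

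| Source | End date |
|---|---|
| Protocol 10.3.3.4 (consent withdrawn; SAE, severe or related) | Date of consent withdrawal |
| SAP 6.2.1, flag Yes or missing | None, unless the patient died |
| SAP 6.2.1, withdrawal or loss to follow-up without end date | Date of last known participation |

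Both SAP rows apply to the same record and no precedence is given. A withdrawn patient can therefore have a related event closed by the site, while an unrelated mild event is left open or closed depending on the programmer.

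**(c) Event over before dosing counted as a TEAE.** First dose 15 March.
- Start: March, day unknown; known end 4 March. Imputed start 15 March, which is 15 − 4 = 11 days after the event ended. Flagged TEAE.

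First dose 18 March 2024, known end 27 February 2024.
- Start: 2024, day and month unknown. Imputed start 18 March. Flagged TEAE.
- Start: completely unknown. The end-date check applies and the imputed start is 1 January 2024. Not a TEAE.

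Less information about the start gives the better answer.

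How often would such an event be caught? Take every first-dose date in 2024 and every onset from Day −30 to Day −1: 366 × 30 = 10,980 pairs, all equally likely by assumption.
- Day missing: the error occurs when onset and first dose share a calendar month. Summing over months, 7 × 465 + 4 × 435 + 406 = 5,401 pairs; 5,401 / 10,980 = 49%.
- Day and month missing: the error occurs when they share a calendar year. Only 30 + 29 + … + 1 = 465 pairs escape; (10,980 − 465) / 10,980 = 96%.

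These shares are conditional on a recorded pre-dose AE with a partial start and a known pre-dose end. They are not shares of all AEs. One patient misclassified in an arm of 8 is 1/8 = 12.5 percentage points.

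**(d) End before onset.** Last dose Day 337; a related AE starts on Day 400; flag No; end date missing. The imputed end is Day 337, which is 400 − 337 = 63 days before onset. This happens for every onset after the last dose:
- Last dose Day 337: 365 − 337 = 28 days to Week 53; 505 − 337 = 168 days to end of study.
- Last dose Day 169 (seventh dose, 1 + 6 × 28): 196 and 336 days, if the patient is followed that far.

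The partial-end rules fail the same way. With last dose 3 February 2025, an event starting 15 February with end February 2025, day unknown, is given an end of 3 February.

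**The case against.** The case for leaving the rules alone is that their reach is small, and much of it stands.

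- **TEAE flags.** A reader might infer that consent withdrawals make the TEAE flags wrong. They do not. TEAE status rests on onset or worsening, so the withdrawal rule and the end-date rules cannot change it. Only (c) can, and it has nothing to do with withdrawal.
- **Listings.** A reader might infer that listings will display imputed recoveries. They will not, because imputed dates are confined to derivations. Only the site-entered withdrawal date in (a) reaches a listing.
- **Indistinguishable events.** A reader might infer that an unresolved SAE cannot be told from a resolved one. The documents do not show that. The SAP relies on an ongoing flag that Protocol 10.3.3.1 does not list, so that list is not the whole eCRF. SAE reports also carry outcome information, and SAP section 7 lists discontinuation dates, so a coincident end date could be spotted.
- **Who is affected.** Declining to re-consent to an extension is not withdrawing consent. SAP section 1 attributes early termination to the former, and section 16 names both. The documents do not say how many patients fall in each group.
- **Rarity of (c).** It needs a pre-dose SAE or procedure-related AE with a partial start and a known pre-dose end. The error over-counts TEAEs.
- **No duration analysis.** Negative durations from (d) enter no planned summary.

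These points limit the consequences but do not repair the rules. It could also be said that the field covers stabilization as well as resolution, but the withdrawal rule requires neither.

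**Conclusion.** The point holds in four limited parts. (a) The protocol's withdrawal rule can show an unresolved serious or related event as ended in planned listings. (b) The SAP's rules for withdrawn or lost patients with ongoing events contradict each other, and the withdrawal rule differs from the protocol; the passages must be reconciled. (c) The two partial-start rules can turn an event known to have ended before dosing into a TEAE. (d) Imputed ends can precede onset, in derived dates only.

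Parts (a) and (c) matter most, because they reach planned outputs. The size per patient is 12.5 percentage points of incidence for (c), assuming the planned 8 per arm. The total effect is unknown: the documents give neither the number of partial dates nor the number of events unresolved at withdrawal. The conclusion is that records can be wrong under the stated rules, not that they are.

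**What to change.** **eCRF completion guideline, and both places in Protocol 10.3.3.4 if it is amended.** For an event unresolved at consent withdrawal, leave the end date blank, mark the event ongoing or outcome unknown, and record the date of last contact.

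**SAP 6.2.1**
1. State that, for AEs of withdrawn or lost patients, the no-imputation rule for a flag of Yes or missing takes precedence. Do not simply delete the withdrawal rule, since events flagged No with no end date would then fall to the last-dose rule.
2. Apply the end-date check of the completely-missing rule to both partial-start rules.
3. Set every imputed end date no earlier than onset.

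**If the protocol is not amended**, flag in the listings any AE end date equal to the consent-withdrawal date.

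**Cost.** A few lines of SAP text, a guideline change and a little programming, best done before database lock. A protocol amendment would need the usual approvals, which may not be worthwhile in a study already ended early; the listing flag covers that case. More events will be shown as unresolved or unknown.

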10.3.4. Reporting of SAEs

The Sponsor has requirements for expedited reporting of SAEs meeting specific criteria to regulatory authorities. Therefore, the Sponsor must be notified immediately regarding any SAE

that occurs after administration of the study drug and any SAE assessed by the PI (or designee) as related to a study procedure that occurs after the participant has signed an ICF.

All SAEs must be reported to the Medical Monitor within 24 hours of the Investigational Site's knowledge of the event. The study site will transmit a SAER using the designated safety mailbox.

An optional initial report can be made via telephone, but a completed SAER must still be faxed or emailed within 24 hours of the site's knowledge of the event. The Investigational Site will be provided with SAER forms wherein the following information is requested. In addition, relevant eCRF pages should be appended to communicate relevant study drug and patient outcome information.

- Patient identification number, PI name, and site number
- SAE information: event term, onset date, severity, and causal relationship
- The outcomes attributable to the event (eg, death, a life-threatening AE, inpatient hospitalization, prolongation of existing hospitalization, a persistent or significant disability or incapacity, or other important medical event[s])
- A summary of relevant test results, pertinent laboratory evaluations, and any other relevant medical history
- The first and last dates of study drug administration. NOTE: as this is a double-masked study, SAERs should not indicate specific study drug assignments
- Indicate if the study drug was discontinued or the study drug administration schedule modified
- Supplemental information may include the following hospital records: laboratory results, radiology reports, progress notes, admission and emergency room notes, holding and observation notes, discharge summaries, autopsy reports, and death certificates

The SAER should be faxed or emailed within 24 hours of the site's knowledge of the event with as much of the above information as available at the time. The following minimum information is required for reporting an SAE: patient identification, reporting source, and an event or outcome. Supplemental information may be transmitted using a FU report and should not delay the initial report. Supplemental information should be marked as a FU report and faxed or emailed using the safety mailbox. The Sponsor may contact the Investigational Site to solicit additional information or follow up on the event.

The PI (or designee) must take all therapeutic measures necessary for resolution of the SAE. Any medications or procedures necessary for treatment of the SAE must be recorded on the appropriate pages of the patient's eCRF. Withdrawal from the study and therapeutic measures taken shall be at the discretion of the PI (or designee). A full explanation for the discontinuation from the study should be made in the patient's medical records and the patient's eCRF.

All SAEs must be reported to the Investigational Site's concerned regulatory authority and/or ethics committee by the PI (or designee) in accordance with its regulations.

10.4. Appendix 4: Contraceptive Guidance

The risks of LASN01 administration during pregnancy have not been evaluated.

Female patients must be nonpregnant nonlactating, and either postmenopausal (ie, no menses for ≥ 12 months without an alternative medical cause and FSH level within the postmenopausal range), surgically sterile (ie, hysterectomy, bilateral salpingectomy, bilateral oophorectomy) for ≥ 6 months, or agree to use a highly effective method of contraception from the start of the study and for ≥ 90 days following the last dose of study drug or until the EOS visit, whichever is later. Male patients must use a highly effective method of contraception unless considered permanently surgically sterile following a bilateral orchidectomy.

Highly effective methods of contraception are:

- Combined (estrogen and progestogen containing) hormonal contraception associated with inhibition of ovulation:
 - Oral
 - Intravaginal
 - Transdermal
- Progestogen-only hormonal contraception associated with inhibition of ovulation:
 - Oral
 - Injectable
 - Implantable
- Intrauterine device (IUD)
- Intrauterine hormone-releasing system (IUS)
- Bilateral tubal occlusion
- Vasectomized partner (having received medical assessment of the surgical success)
- True sexual abstinence from the start of the study and for ≥ 90 days following the last dose of study drug or until the EOS visit, whichever is later, is acceptable only when refraining from heterosexual intercourse during the entire period of risk associated with the study treatment, as described above. The reliability of sexual abstinence needs to be evaluated in relation to the duration of the clinical trial and the preferred and usual lifestyle of the patient. Periodic abstinence (calendar, symptothermal, postovulation methods), withdrawal (coitus interruptus), spermicides only, and lactational amenorrhea methods are not considered “true” abstinence and are not acceptable methods of contraception

The contents of this document are confidential to [REDACTED]
 Unauthorized use, disclosure, or reproduction is strictly prohibited.

13.2	LASN01 Pharmacokinetics	34
13.3	Statistical Assessment of Dose-Proportionality	35
14.	Pharmacodynamic Analyses	35
15.	Interim Analyses	36
16.	Changes from Protocol-Stated Analyses	36
17.	References	37
18.	Final Analysis Tables, Listings and Figures	37
18.1	Tables	37
18.2	Listings.....	40
18.3	Figures.....	42
19.	Appendix: Schedule of Assessments and Procedures	44
19.1	Schedule of Assessments and Procedures – Treatment Period.....	44
19.2	Schedule of Assessments and Procedures – Follow-up Period	49

CONFIDENTIAL

The contents of this document are confidential to [REDACTED]
Unauthorized use, disclosure, or reproduction is strictly prohibited.

List of Abbreviations

Abbreviation	Definition
ADA	Anti-drug Antibodies
AE	Adverse Event
ANCOVA	Analysis of Covariance
AUC _{0-∞}	Area under the concentration time curve from time 0 extrapolated to time infinity
AUC _{0-28d}	Area under the concentration time curve from time 0 to 28 days postdose
AUC _{0-last}	Area under the concentration time curve from time 0 to the timepoint with the last measurable concentration
BCVA	Best-Corrected Visual Acuity
BMI	Body Mass Index
CAS	Clinical Activity Score
CI	Confidence Interval
CL	Clearance
C _{max}	Maximal concentration
C _{min}	Minimal concentration
CS	Clinically Significant
CT	Computed Tomography
CTMS	Clinical Trial Management System
CV	Coefficient of Variation
DMP	Data Management Plan
ECG	Electrocardiogram
eCRF	Electronic Case Report Form
EOS	End of Study
ETDRS	Early Treatment of Diabetic Retinopathy Study
HR	Heart Rate
IA	Interim Analysis
ICH	International Conference on Harmonisation
IL	Interleukin
IOP	Intraocular Pressure
IV	Intravenous(ly)
λ_z	Terminal elimination rate constant
LOCF	Last Observation Carried Forward
LS	Least Squares

CONFIDENTIAL

The contents of this document are confidential to [REDACTED]
 Unauthorized use, disclosure, or reproduction is strictly prohibited.

Abbreviation	Definition
MedDRA	Medical Dictionary for Regulatory Activities
MMRM	Mixed Model Repeated Measures
MRD1	Margin reflex distance 1
MRD2	Margin reflex distance 2
MRI	Magnetic Resonance Imaging
NCA	Noncompartmental Analyses
NCS	Not Clinically Significant
ODO	Observed Data Only
Q4W	Every 4 Weeks
PCR	Polymerase Chain Reaction
PD	Pharmacodynamics
PDF	Portable Document Format
PI	Principal Investigator
PK	Pharmacokinetics
PT	Preferred Term
QTcF	QT Interval Corrected by Fridericia's Formula
RTF	Rich Text Format
SAP	Statistical Analysis Plan
SD	Standard Deviation
SE	Standard Error
SOC	System Organ Class
SRC	Safety Review Committee
$t_{1/2}$	Terminal half-life
TEAE	Treatment-Emergent Adverse Event
TED	Thyroid Eye Disease
T_{last}	Time point with the last measurable concentration
TLF	Tables, Listings and Figures
T_{max}	Time at which the maximal concentration is observed
TSH	Thyroid Stimulating Hormone
TSI	Thyroid Stimulating Immunoglobulin
V_{ss}	Steady-state volume of distribution
V_z	Volume of distribution based on the terminal phase
WHODrug	World Health Organization Drug Dictionary

CONFIDENTIAL

The contents of this document are confidential to [REDACTED]
 Unauthorized use, disclosure, or reproduction is strictly prohibited.

1. Introduction

This statistical analysis plan (SAP) details the planned analyses and reporting for protocol LASN01-CL-2201, with the United States Version 7.0 dated 15NOV2024, and the European and UK Version 7.1 dated 22NOV2024. The statistical methods herein supersede those in the clinical protocol. Any additional required analyses will be completed and identified in the clinical study report.

This SAP has been prepared with consideration of the latest International Conference on Harmonisation (ICH) E9 Guideline, "Guidance for Industry: Statistical Principles for Clinical Trials," and the latest ICH E3 Guideline, "Guidance for Industry: Structure and Content of Clinical Study Reports."

This study was conducted as proof of concept for evaluation of role of IL-11 in thyroid eye disease (TED). TED trials have assigned a target eye, traditional to trials that deliver drug to one eye. As LASN01 is being administered systemically, there should be no difference between either eye and response in either eye should be considered. Procedurally, the protocol has used the target eye as primary endpoint, however, as the study is signal seeking in nature, the drug is administered systemically (intravenously [IV]), and response in either eye is evaluated in consideration of response. A substantial number of patients did not reconsent to protocol v7.0/7.1, which led to the early termination of the study. Only the primary endpoint (proptosis responder) and total 7-point Clinical Activity Score (CAS; Total CAS) endpoints will be summarized. Other exploratory or secondary endpoints will not be analyzed and the per protocol population has been removed.

2. Study Objectives and Endpoints

Objectives	Corresponding Endpoints
Primary: Efficacy	
To assess changes in proptosis following IV administration of 2 dose levels of LASN01 in patients with TED	
For randomized treatment arms:
 
 Percentage of patients who have received LASN01 (pooled analysis of 300 and 600 mg every four weeks [Q4W]) showing a response in proptosis (≥ 2 mm decrease from Baseline) in the study eye and separately in either eye without deterioration (≥ 2 mm increase) of proptosis in the fellow eye at Week 37 following treatment with IV LASN01 compared with placebo

CONFIDENTIAL

The contents of this document are confidential to [REDACTED]
Unauthorized use, disclosure, or reproduction is strictly prohibited.

Secondary: Efficacy	
To assess changes in TED-related clinical parameters following IV administration of LASN01 in patients with TED	
For randomized treatment arms:
 
 Percentage of patients who have received LASN01 (600 mg Q4W) showing a response in proptosis (≥ 2 mm decrease from Baseline) in either eye without deterioration (≥ 2 mm increase) of proptosis in the other eye at Weeks 17, 21, 25, 29, 33, 37, 41, 45, 49, 53, 57, 65, and 73 following treatment with IV LASN01 compared with placebo Percentage of patients who have received LASN01 (300 mg Q4W) showing a response in proptosis (≥ 2 mm decrease from Baseline) in either eye without deterioration (≥ 2 mm increase) of proptosis in the other eye at Weeks 17, 21, 25, 29, 33, 37, 41, 45, 49, 53, 57, 65, and 73 following treatment with IV LASN01 compared with placebo Percentage of patients who have received LASN01 (pooled analysis of 300 and 600 mg Q4W) showing a response in proptosis (≥ 2 mm decrease from Baseline) in either eye without deterioration (≥ 2 mm increase) of proptosis in the other eye at Weeks 17, 21, 25, 29, 33, 41, 45, 49, 53, 57, 65, and 73 following treatment with IV LASN01 compared with placebo Mean change from Baseline in proptosis in patients who have received LASN01 (600 mg or 300 mg Q4W) compared with placebo at Weeks 17, 21, 25, 29, 33, 37, 41, 45, 49, 53, 57, 65, and 73 Changes in TED-related clinical parameters (CAS) across both LASN01 treatment arms (pooled analysis of 300 and 600 mg Q4W) and in each individual LASN01 treatment arm (600 mg or 300 mg Q4W) compared with placebo at Weeks 17, 21, 25, 29, 33, 37, 41, 45, 49, 53, 57, 65, and 73
Primary: Safety	
To assess the safety and tolerability of IV administration of LASN01 compared with placebo in patients with TED	
For randomized treatment arms:
 
 Treatment-emergent adverse events (TEAEs), changes in concomitant medications compared with placebo Changes from Baseline in clinical laboratory evaluations, vital signs, electrocardiograms, ophthalmic assessments, and physical

CONFIDENTIAL

The contents of this document are confidential to [REDACTED]
 Unauthorized use, disclosure, or reproduction is strictly prohibited.

	
examinations following study drug administration compared with placebo
 
For open-label treatment arm(s):
 
 • TEAEs, changes in concomitant medications • Changes from Baseline in clinical laboratory evaluations, vital signs, electrocardiograms, ophthalmic assessments, and physical examinations following study drug administration
Secondary: Pharmacokinetics	
To characterize the pharmacokinetic (PK) profile of IV administration of LASN01 in patients with TED	
For all treatment arms:
 
 • Serum LASN01 concentrations at specified time points
Exploratory: Immunogenicity	
Characterize the immunogenicity of IV administration of LASN01 in patients with TED	
For all treatment arms:
 
 • Incidences of antidrug antibodies at specified timepoints relative to Baseline
Exploratory: Pharmacodynamics	
To explore the potential pharmacodynamic profile of IV administration of LASN01 in patients with TED	
For all treatment arms:
 
 • Protein markers in blood relevant to the Interleukin-11 (IL-11) pathway

